5.2.2 Exclusion Criteria

Patients will be excluded if they meet any of the exclusion criteria listed below:

1. Previous exposure to OTL38
2. Any medical condition that in the opinion of the investigators could potentially jeopardize the safety of the patient
3. History of anaphylactic reactions to folate, including synthetic folic acid (pteroylmonoglutamic acid) and contrast agents containing indocyanine green for near

infrared imaging. Patients with a medical history of 'idiopathic anaphylaxis' will require evaluation.

4. History of allergy to any of the components of OTL38, including folic acid
5. A positive serum pregnancy test at Screening or a positive urine pregnancy test on the day of surgery or day of admission for female subjects of childbearing potential
6. Clinically significant abnormalities on electrocardiogram (ECG) at screening.
7. Presence of any psychological, familial, sociological condition or geographical challenges potentially hampering compliance with the study protocol and follow-up schedule
8. Impaired renal function defined as $eGFR < 50 \text{ mL/min/1.73m}^2$
9. Impaired liver function defined as values $> 3x$ the upper limit of normal (ULN) for alanine aminotransferase (ALT) or aspartate aminotransferase (AST), alkaline phosphatase (ALP), or $> 2x$ ULN for total bilirubin excluding those patients with Gilbert's syndrome.
10. Received an investigational agent in another investigational drug or vaccine trial within 30 days prior to the administration of study drug
11. Known sensitivity to fluorescent light

5.3 Study Assessments

The assessments for this study are listed in [Section 5.8](#).

5.4 Patient Discontinuation Criteria

Although a single dose of study drug is infused on Day 1, a patient may be withdrawn from the study for any of the following reasons:

- Request of the patient or patient's representative
- AEs or adverse device effects (ADEs) based on the judgment of the Investigator
- The Investigator decides that it is in the patient's best interest
- The patient is noncompliant with the protocol
- Lost to follow-up
- Death

If a subject is withdrawn at any time, the reason(s) will be recorded on the relevant page of the electronic case report form (eCRF).

Patients discontinued due to AEs or ADEs will be monitored until resolution or stability of the event based on the judgment of the investigator.

5.5 Replacement of Dropouts

Subjects withdrawing or dropping out prior to completion of Visit 2b (surgery) will be replaced.

5.6 Study Drug Information and Dosage

5.6.1 Identification and Description of Test Article

OTL38 will be supplied in vials containing 1.6 mL of solution of 2 mg/mL OTL38 for a total of 3.2 mg of drug per vial. The contents of the vial are a frozen blue-green solution.

5.6.2 Packaging and Labeling

The study medication will be packaged in vials and labelled by the Sponsor's clinical supplies designee.

The labels will include:

Name and contact information for the Sponsor:

On Target Laboratories, Inc.
[REDACTED]

Route of administration: injection

Quantity supplied: 3.2 mg OTL38 per vial

Pharmaceutical dosage form: [REDACTED]

Storage conditions: keep frozen [REDACTED]

CAUTION: New Drug – Limited by Federal Law To Investigational Use

Lot number

Manufacturing date in day/month/year format.

Retest or Expiration date in day/month/year format

5.6.3 Storage and Handling of Test Article

The study medication will be packaged in vials and labelled by the Sponsor's clinical supplies designee.

Study medication should be stored [REDACTED] and with protection from light (see Site Study Reference Manual).

A Research Pharmacist or other trained and qualified healthcare professional will prepare the IV solutions according to instructions provided by On Target Laboratories at the assigned dose. All prepared solutions should be protected from light and refrigerated (between 2-8°C) until use (see Site Study Reference Manual).

5.6.4 Study Drug Administration

OTL38 will be prepared following the Dose Preparation for OTL38 Injection Pharmacy Manual. OTL38 will be administered intravenously over approximately 60 minutes.

[REDACTED]

[REDACTED]

5.6.5 Camera/Imaging System

The imaging systems used in this study are not approved for use with OTL38, and are therefore considered investigational for the purposes of this study. Technical data for the [REDACTED] [REDACTED] The imaging system used for each subject will be recorded in the eCRF.

5.6.6 Training Requirements

At each site, investigators will image their first eligible patient meeting inclusion and exclusion criteria under the guidance of personnel trained in the use of the imaging agent and NIR camera system. The purpose of this training is to ensure correct use and operation of the camera system.

5.6.7 Tumor to Background Ratio

For cameras that are capable of doing so, tumor-to-background ratio will be calculated for each patient for comparison [REDACTED]

[REDACTED]

[REDACTED]

5.6.7.1 Summary of the Camera/Imaging System Requirements

[Redacted text block]

[Redacted text block]

[Redacted text block]

[Redacted text block]

[REDACTED]

5.6.7.2 Quality System Requirements

On Target Laboratories outsources design and contract manufacturing for the final device and its labeling, and packaging. As part of the On Target Laboratories Supplier Approval Process, the contract manufacturer’s quality system and compliance with the following federal and international regulations are assessed:

- USA 21 CFR Part 820: Code of Federal Regulations, Quality System Regulations; current edition
- ISO 13485:2003 Medical Devices – Quality management systems – Requirements for regulatory purposes
- Medical Device Directive: Council Directive 93/42/EEC concerning medical devices

5.7 Prior and Concomitant Medications

5.7.1 Prior Medications

Prior medications will include all recorded medications and supplements a patient was taking during the screening period that were stopped prior to administration of the study drug. These should be recorded in the eCRF.

5.7.2 Allowed Medications

Necessary supportive measures for optimal medical care will be given throughout the study. Additional care may be administered as indicated at the discretion of the treating physician, and where appropriate after discussion with the medical monitor.

5.7.3 Concomitant medications

Concomitant medications will include all medications that started, or were continuing, during or after administration of the study drug. All concomitant medications and supportive therapy administered starting Day 1 prior to the infusion of OTL38 until the final study visit must be recorded on the appropriate case report form (eCRF).

5.7.4 Prohibited Medications

No other investigational products will be allowed 30 day prior to study drug administration. If the patient is on any folate supplement (including multi-vitamin supplements or pre-natal vitamins), the patient will need to stop taking the supplement 48 hours before scheduled drug infusion.

5.8 Schedule of Events

5.8.1 Measurement and Evaluations

Please see [Schedule of Assessments](#) for a detailed study schedule, including all measurements and evaluations for the entire study period (Screening to Follow-up) presented in tabular form.

5.8.1.1 Visit 1 (Screening, up to Day -28)

Prior to the initiation of study-specific screening assessments the Investigator or designee must provide the patient(s) a complete explanation of the purpose and evaluations (procedures and assessments) of the study. Subsequently, the patient must sign and receive a copy of an Informed Consent Form and authorization of use and disclosure of protected health information (PHI) that was approved by the institutional review board (IRB). Once informed consent has been obtained, the eligibility of the patient will be determined, and Screening Period assessments will be performed.

- Signed informed consent
- Complete medical history including diagnosis or suspicion of lung nodules by CT/PET/MRI.
- Physical examination
- Height and weight

- Prior medication assessment
- Vital signs (temperature, blood pressure, and pulse rate)
- Serum Pregnancy test (for women of childbearing potential)
- 12-lead ECG
- Clinical laboratory assessments including hematology, chemistries, and urine analysis

5.8.1.2 Visit 2- (Day 0 and/or 1)

Study drug infusion can optionally occur the day before surgery

Day 0 or 1 – Infusion (Visit 2a)

- Updated medical history
- Physical exam
- Prior and concomitant medications assessment
- Clinical laboratory and vital sign assessments will be performed prior to infusion.
- Urine pregnancy test (for women of childbearing potential) prior to infusion.
- 12-lead ECG will be collected at least 15 minutes prior to infusion, and at least 15 minutes prior to surgery after infusion of OTL38 is completed
- A single dose of OTL38 will be infused IV over 60 minutes and will be completed [REDACTED] to initiation of intraoperative imaging and the time will be recorded
- AEs will be recorded during infusion of OTL38
- [REDACTED]

Day 1 – Surgery (Visit 2b)

- [REDACTED]
- [REDACTED]
- [REDACTED]
- [REDACTED]
- [REDACTED]

- █ [REDACTED]
- █ [REDACTED]

[REDACTED]

[REDACTED]

[REDACTED]

[REDACTED]

- █ [REDACTED]
- █ [REDACTED]
- █ [REDACTED]
- █ [REDACTED]
- █ [REDACTED]

[REDACTED]	[REDACTED]

- █ [REDACTED]
- █ [REDACTED]

[Redacted]

[Redacted]

- [Redacted]

[Redacted]

- [Redacted]

[Redacted]

- [Redacted]

[REDACTED]

■ [REDACTED]

5.8.1.3 Visit 3-Follow-up (Day 7 [± 4])

- Follow-up will be scheduled for Day 7 (± 4) on site
- AEs, ADEs, and concomitant medication information will be recorded.
- Clinical laboratory and vital sign assessments will be performed.

5.8.1.4 Visits 4-Follow-up (Day 28 [±4])

- Follow-up will be scheduled for Day 28 (±4) either via patient telephone interview or clinic visit
- AEs, ADEs, and concomitant medication information will be collected.

5.8.2 Surgical Reporting Schematics

[REDACTED]

[REDACTED]

[REDACTED]

[REDACTED]

5.8.3 Investigator Post-Surgery Questionnaire (Visit 2b)

After each surgery, the Investigator will fill out the questionnaire located within the study reference manual at the conclusion of each case.

5.8.4 Pathology Samples

All excised lesions will be processed as outlined in “Post-Surgery Tissue Processing”. Please refer to the Study Reference Manual for additional details.

5.8.5 Camera/Imaging System Exposure (NIR Fluorescent Imaging Group Only)

A camera/imaging system will be used to identify tumor lesions under fluorescence prior to surgical excision of lesions, and again after surgical excision of lesions to identify persistent lesions. The Investigator will record the start and stop time for each in situ exposure to fluorescence imaging (pre-resection, post-initial resection, other [give reason]) in the eCRF. The total time of fluorescence will be calculated automatically.

Back table imaging will not be included in the fluorescence exposure time.

Status	Time On Fluorescent Light	Time Off Fluorescent Light
Before surgical excision		
After initial surgical excision		
Other (explain reason)		

6 STUDY ENDPOINTS

6.1 Primary

The primary efficacy endpoint is the proportion of FAS subjects who have a Clinically Significant Event (CSE). A CSE is defined as at least one of the following outcomes:

[REDACTED]

6.2 Secondary

The secondary efficacy endpoints are:

1. Sensitivity and False Positive Rate [REDACTED]
- [REDACTED]

cancer in the lung defined as the proportion of fluorescent light positive FR+ primary

[REDACTED]

4.

[REDACTED]

[REDACTED]

[REDACTED]

6.3 Exploratory

[REDACTED]

[REDACTED]

6.4 Safety

1. Incidence rates of all treatment-emergent AEs (TEAEs), adverse device effects (ADEs), and SAE's. Treatment-emergent adverse events (TEAEs) are defined as starting, during or after exposure to study drug.
2. Evaluation of laboratory parameters (chemistry and hematology) and vital signs
3. Evaluation of Electrocardiograms (ECG) before and after study drug administration

7 PROCEDURES FOR REPORTING ADVERSE EVENTS

7.1 Adverse Events Definitions

The Investigator will monitor the occurrence of AEs during the course of the study that will end with Visit 4.

The following definitions of terms are guided by the United States Code of Federal Regulations (21 CFR 312.32(a)) and are included here.

Adverse event is any untoward medical occurrence in a patient associated with the use of a drug in humans, whether or not considered drug related.

Suspected adverse reaction means any adverse event for which there is a reasonable possibility that the drug caused the adverse event. For the purposes of IND safety reporting, "reasonable possibility" means there is evidence to suggest a causal relationship between the drug and the adverse event. Suspected adverse reaction implies a lesser degree of certainty about causality than adverse reaction, which means any adverse event caused by a drug.

Unexpected adverse event (adverse drug experience) or (suspected) adverse reaction means any adverse event or (suspected) adverse reaction that is not listed in the investigator brochure or is not listed at the specificity or severity that has been observed.

An AE or suspected adverse reaction is considered "serious" if, in the view of either the investigator or sponsor, it results in any of the following outcomes: Death, a life-threatening adverse event, inpatient hospitalization or prolongation of existing hospitalization, a persistent or significant incapacity or substantial disruption of the ability to conduct normal life functions, or a congenital anomaly/birth defect. Important medical events that may not result in death, be life-threatening, or require hospitalization may be considered serious when, based upon appropriate medical judgment, they may jeopardize the patient and may require medical or surgical intervention to prevent one of the outcomes listed in this definition.

An adverse event is considered "life-threatening" if, in the view of either the investigator or sponsor, its occurrence places the patient at immediate risk of death. It does not include an adverse event that, had it occurred in a more severe form, might have caused death.

Suspected Unexpected Serious Adverse Reaction (SUSAR) is any (suspected) adverse reaction (any adverse event for which there is a reasonable possibility that the drug caused the adverse event) that is both serious and unexpected.

7.2 Adverse Device Effects Definitions

7.2.1 Adverse Device Effect

An ADE is defined as any untoward and unintended response to a medical device, in this study, the camera/imaging system. This definition includes any event resulting from insufficiencies or inadequacies in the instructions for use or the deployment of the device, as well as any event that is the result of a user error [ISO 14155-1:2003 (E) 3.1].

All ADEs noted during the study will be reported in the eCRF.

7.2.1.1 Suspected Adverse Device Effect

A suspected ADE is a subset of all ADEs for which there is a reasonable possibility (i.e., evidence to suggest a causal relationship between the device and the ADE) that the device caused the event. Suspected ADE implies a lesser degree of certainty about causality than adverse device effect.

7.2.1.2 Unanticipated Adverse Device Effect

An unanticipated ADE is any serious adverse effect on health or safety or any life-threatening problem or death caused by, or associated with, a device, if that effect, problem, or death was not previously identified in nature, severity, or degree of incidence in the investigational plan or application, or any other unanticipated serious problem associated with a device that relates to the rights, safety, or welfare of subjects [21 CFR 812.3 (s)].

7.3 Reporting of Adverse Events

7.3.1 Adverse Events

The safety of all patients enrolled in this study will be recorded from the time of study drug administration and throughout the course of the study that will end with Visit 4.

All AEs will be recorded in the appropriate section of the eCRF. Patients withdrawn from the study because of AEs will be followed by the investigator until the outcome is determined. When appropriate, additional written reports and documentation will be provided.

All AEs beginning during or after the exposure to study drug must be reported to the sponsor or its designee if the onset of the AE was before Visit 4. All AEs that are judged by the investigator to be not related to study drug need not be reported to the sponsor or its designee after Visit 4. All AEs that are judged by the Investigator to be related to study drug administration must be reported to the sponsor or its designee regardless of how much time has elapsed since the last exposure to study drug.

7.3.2 Laboratory Abnormalities

To the extent possible, all clinically significant laboratory abnormalities observed during the course of the study will be included under a reported AE describing a clinical syndrome (e.g., elevated blood urea nitrogen and creatinine in the setting of an AE of “renal failure” or elevated ALT/AST in the setting of an AE of “hepatitis”). In these cases (e.g., an AE of renal failure), the laboratory abnormality itself (e.g., elevated creatinine) does not need to be recorded as an AE.

In the absence of a reported AE identifying a clinical syndrome that encompasses the observed clinically significant laboratory abnormality that “isolated” laboratory abnormality itself should be reported as an AE.

Patients experiencing AEs or laboratory abnormalities will be assessed and appropriate evaluations performed until all parameters have returned to baseline levels, or are consistent with the patient’s then-current physical condition, in the opinion of the investigator.

7.3.3 Serious Adverse Events

Instructions for reporting Serious Adverse Events (SAE) and Suspected Unexpected Serious Adverse Reactions (SUSAR) are found on [Page 2](#). A written report of all SAEs that occur after the administration of study drug and during the study (ending with Visit 4) must be submitted to the IRB/ethics committee (EC) and the Sponsor. SAEs/SUSARs must be reported to the Sponsor within 24 hours for a determination of expedited reporting to FDA, as described in [Section 7.7](#). In all SAE reports, the investigator will advise whether or not the SAE is judged to be related to study drug administration. SAEs that occur after Visit 4 and are not reasonably associated with study drug do not require reporting per the instructions given below. All SAEs that are judged by the investigator to be at least possibly related to study drug administration must be reported to the sponsor or its designee regardless of how much time has elapsed since the last exposure to study drug. All SAEs must be submitted to the IRB/EC in an annual report per local reporting guidelines.

7.3.4 Reporting of Pregnancies

If a patient becomes pregnant during the course of the study, the investigator or site personnel must notify the Medical monitor (see [Page 2](#) for details) within 5 working days after the investigator or site personnel become aware of the pregnancy. If an SAE occurs in conjunction with the pregnancy, then the reporting time frame for an SAE must be met.

7.3.5 Disease Progression

The progression of lung cancer (in patients diagnosed as such) per se will not constitute an AE. However, if the progression of the lung cancer meets the criteria for an SAE, then it should be reported as an SAE (see [Page 2](#)).

7.4 Overdoses

Overdoses should be reported as a protocol violation. If an overdose results in an AE, the CRF AE page should be completed, and source documents included. If the overdose results in an SAE, then SAE reporting should be followed using the specific CRF pages with overdose information entered in the narrative section. All available clinical information relevant to overdose, including signs and symptoms, laboratory findings, and therapeutic measures or treatments administered, should be summarized and discussed.

7.5 Classification of Adverse Events by Severity

The investigator must categorize the severity of each AE according to the following:

- Mild: Awareness of signs or symptoms, but easily tolerated and are of minor irritant type. Symptoms do not require therapy or a medical evaluation; signs and symptoms are transient.

- Moderate: Events introduce a low level of inconvenience or concern to the participant, but are usually improved by simple therapeutic measures; moderate experiences may cause some interference with functioning
- Severe: Events generally require systemic drug therapy or other treatment; they are usually incapacitating
- Life-Threatening: Risk of imminent death requiring immediate intervention.

7.6 Classification of Adverse Events by Relationship to Study Drug Administration

The relationship of each AE to the study drug administration will be assessed by the investigator; after careful consideration, according to the following guidelines:

Related: An adverse event that has a timely relationship to the administration of the study drug and follows a known pattern of response for which no alternative cause is present or may be excluded.

Possibly Related: An adverse event that has a timely relationship to the administration of the study drug, follows no known pattern of response, but a potential alternative cause does not exist

Not related: An adverse event for which there is evidence that it is definitely related to a cause other than the study; in general, no timely relationship to the administration of the drug exists, or if so, the event does not follow a pattern of response and an alternative cause is present

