14.3 Adverse Events

Adverse events that are not treatment-emergent, those occurring after signing the ICF but prior to exposure to OTL38 administration, will be provided in line listings. Treatment emergent adverse events (TEAEs) will be summarized via the Medical Dictionary for Regulatory Activities (MedDRA) system organ class and preferred term using subject incidence rates. Data will be tabulated by severity, physician assessment of relationship to study drug, serious TEAEs, and TEAEs leading to death or early study withdrawal. Further description of TEAEs may be defined by temporal onset to study drug infusion and/or by event incidence. Additional summaries of TEAEs identified as potential ADEs will also be provided for those subjects exposed to imaging.

Treatment-emergent AEs will be summarized for all subjects in the Safety Analysis Set (SfAS). Summary tables will reflect the number and percent of subjects experiencing at least 1 TEAE in each system organ class and preferred term. The overall number and percent of subjects

experiencing any treatment-emergent AE will also be provided. All percentages will use the number of subjects in the SfAS set as the denominator. An exception will be the presentation of ADEs which will use all subjects undergoing fluorescent light imaging as the denominator. If a subject has more than one AE within a system organ class, the subject will be counted only once in that system organ class. If a subject has more than 1 AE that codes to the same preferred term, the subject will be counted only once for that preferred term.

Treatment-emergent AEs will also be summarized by the maximum relationship to study drug as determined by the Principal Investigator as well as the maximum severity of the event. Relationship to study drug will be scored as Related, Possibly Related, or Not Related. Related AEs will be classified as those scored as Related or Possibly Related. Severity will be rated as per CTCAE v5.0:

- Grade 1 Mild; asymptomatic or mild symptoms; clinical or diagnostic observations only; intervention not indicated.
- Grade 2 Moderate; minimal, local or noninvasive intervention indicated.
- Grade 3 Severe or medically significant but not immediately life-threatening; hospitalization or prolongation of hospitalization indicated; disabling;
- Grade 4 Life-threatening consequences; urgent intervention indicated.
- Grade 5 Death related to AE

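### Protocol 7.6 leaves some timely adverse events with a possible but unproven other cause without a relatedness category

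*Protocol*

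**What the plan says.** Protocol 7.6 gives three categories, offered as guidelines for the investigator's assessment.

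- **Related:** timely, and the event "follows a known pattern of response for which no alternative cause is present or may be excluded".
- **Possibly Related:** timely, and the event "follows no known pattern of response, but a potential alternative cause does not exist"; all of these conditions must hold.
- **Not related:** the leading condition is "An adverse event for which there is evidence that it is definitely related to a cause other than the study". A further clause, introduced as holding in general, adds that the event is not timely or, if it is, that "the event does not follow a pattern of response and an alternative cause is present".

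Protocol 7.1 defines a suspected adverse reaction as "any adverse event for which there is a reasonable possibility that the drug caused the adverse event". For IND safety reporting it says that a reasonable possibility "means there is evidence to suggest a causal relationship between the drug and the adverse event".

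SAP 14.3 uses the same three scores without redefining them and pools two of them: "Related AEs will be classified as those scored as Related or Possibly Related". If the relationship is missing, it assumes the maximum relationship for tabulation. One of its five routes to an adverse event of special interest (AESI) also uses the score: events without a start time that begin and end on Study Day 1 and are scored Related or Possibly Related.

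**The concern.** The middle category of a three-point causality scale normally holds events for which the drug is a plausible cause and something else is too. Here it excludes them, because any potential alternative cause bars Possibly Related. The question is whether Related and Not related between them take up everything that is excluded.

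The point matters in this trial because all subjects are expected to receive OTL38 (SAP 5) and surgery follows on the day of infusion or the next day (Protocol 5.8.1.2). A possible competing cause is therefore to be expected for timely post-operative events. With no untreated group anticipated, attribution to the drug leans heavily on this score. If the scale does not place such events, two sites can score the same event differently and both can claim to follow the protocol.

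**Working it through.** There is no figure in the plan to reproduce. The check treats the three definitions as conditions and asks which timely events meet none of them.

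**Inputs (all Protocol 7.6).** For a timely event: whether it follows a known pattern, and whether another cause is absent, possible but excludable, possible and not excludable, or established.

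**Points on which the wording can be read differently.**

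1. 'Present' under Related covers merely possible causes, or only identified ones (2 readings).
2. The same choice for 'present' under Not related (2).
3. The words on exclusion under Related do or do not admit an event whose possible other cause can be excluded (2).
4. Not related needs definite evidence plus the general clause, needs definite evidence alone, or is met by either (3).

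This gives 2 × 2 × 2 × 3 = 24 readings. In 12 of them 'present' has the same meaning in both categories; in the other 12 it does not.

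**The critical cells: timely, with a possible other cause that cannot be excluded.**

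| Pattern | 'Present' means | Related? | Possibly Related? | Not related? |
|---|---|---|---|---|
| Known | includes possible | No: cause present, not excluded | No: pattern known, potential cause exists | No: not definite, follows a pattern |
| Known | identified only | Yes | No | No |
| None | includes possible | No: no pattern | No: potential cause exists | Only if the general clause suffices |
| None | identified only | No: no pattern | No: potential cause exists | No: not definite, no cause present |

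**Results.**

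- 'Present' includes possible causes in both places (6 readings): the known-pattern event whose possible cause cannot be excluded is always unplaced. In 4 of the 6, where the general clause does not suffice, the no-pattern event is unplaced as well.
- 'Present' means identified in both places (6 readings): the no-pattern event with a merely possible cause is always unplaced.
- So 6 + 6 = 12 of 12 consistent readings have a gap.
- Of the 12 mixed readings, 2 close it. Both need 'present' to mean identified under Related and to include possible causes under Not related, and both need definite evidence not to be required.

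Even in those 2 readings, Possibly Related holds only timely, no-pattern events with no potential other cause. That is a different test from 7.1, which asks whether evidence points to the drug and does not require other causes to be absent.

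**Effect on the tables.** Take one unplaced event. Scored Possibly Related, it enters the related-TEAE table. Scored Not related, it does not. Left blank because nothing fits, it enters as related under the SAP's missing-score rule.

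**The case against.** **These are guidelines, not an algorithm.** The section leaves the decision to careful judgement and hedges Not related as holding in general. This stands: events will still be scored. The harm is therefore inconsistent scoring, not unscored events.

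**Surgery is an identified exposure, so an alternative cause is 'present'.** A timely, no-pattern post-operative event can then go to Not related through the general clause. This stands for such events and narrows the gap. It does not help a known-pattern event: the same use of 'present' keeps it out of Related unless surgery can be excluded, and the general clause requires that there be no pattern. Surgery is also not a candidate cause for events during the infusion, which precedes it.

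**The negation may be a drafting slip.** The word 'but' suggests that the opposite was meant. That is a reason to correct the text. Removing the negation alone would not be enough, because a timely, no-pattern event with no other cause would then have no category.

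**Unseen instructions may settle it.** The eCRF completion guidelines (Protocol 8.1) are not among the documents and may say more. Nothing in the protocol or SAP does.

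**Stronger readings that a reader might infer are not supported.**

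- *Safety reporting is compromised.* Reporting of AEs and SAEs through Visit 4 does not depend on the score (Protocol 7.3.1, 7.3.3), SAEs go to the sponsor within 24 hours, and suspected unexpected serious adverse reactions are defined by the 7.1 standard. After Visit 4 reporting does depend on relatedness, but later events will rarely be timely, so the effect is marginal.
- *Drug-related events will be undercounted.* The text does not fix a direction. Depending on the reading or the investigator, the event may be scored Related, scored Not related, or left blank and counted as related.
- *The phase 2 lung results show the size.* Protocol 3.3.5 gives neither the relatedness scale used there nor the event timing needed to identify gap events.

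**Conclusion.** The concern holds in a limited form. As written, and with one meaning of 'present', Protocol 7.6 has no category for at least one kind of timely event with a possible but unproven other cause. Which kind depends on that meaning.

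The outputs affected are the descriptive related-TEAE table and one of the five AESI routes. The primary endpoint, the all-cause TEAE tables, the other four AESI routes and AE/SAE reporting through Visit 4 are not affected. SAP 14.3 offers a partial cross-check that does not use the score, but only as an option: "Further description of TEAEs may be defined by temporal onset to study drug infusion".

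The number of events affected and the direction of any shift cannot be derived from the documents; counts of readings are not event frequencies. The conclusion assumes that the eCRF completion guidelines do not already supply the missing rule. This is a wording fault that should be corrected because it blurs a safety output. It does not threaten the trial's main result.

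**What to change.** Amend Protocol 7.6 so that the categories are applied in this order and cover every event:

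1. **Related:** timely, known pattern, and either no alternative cause identified or any such cause excluded.
2. **Possibly Related:** does not meet Related, but there is a reasonable possibility, by the 7.1 standard, that the drug caused the event, whether or not a known pattern is followed and even if another cause is also possible.
3. **Not related:** no reasonable possibility that the drug caused the event.

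An event that fails the first step either has a reasonable possibility or does not, so exactly one category applies. Using 'identified' in place of 'present' removes the ambiguity.

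Align the eCRF completion guidelines with this wording and send sites a short notice. Re-check adverse events already scored under the old wording, so that two standards are not mixed in one table.

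The cost is the amendment, the notice and that re-check. No data field or SAP table changes. The downside is that the related-TEAE rate may be somewhat higher and less specific, because some timely post-operative events would be scored Possibly Related.
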